7.1 Dose modifications of Nelfinavir and Chemotherapy during Radiotherapy

7.1.1 Hematologic toxicities

Because Grade III hematologic toxicity occurs in approximately 50% of patients receiving combined chemoradiotherapy alone for head and neck cancer and no hematologic toxicity was seen in phase I/II trials of nelfinavir in the setting of HIV patients (34), the dose modifications for hematologic toxicity will be reduction in standard chemotherapy dose. , as per the treating medical oncologist. Hematologic toxicities are expected and will not be followed as part of this trial. They will be managed by the treating medical oncologist.

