agent, nelfinavir, has been widely used in HIV patients with well-characterized pharmacokinetics and low toxicity profile. NFV inhibits the PI3K/Akt/mTOR pathway, which we believe increases the intrinsic radiosensitivity of cells (9-11). However, the effects of NFV on the *in vivo* radiation response appear to be greater than those seen *in vitro*, which led us to investigate whether the drug might have effects on the tumor microenvironment (TME) that could improve the radiation response. Indeed, we and others have found that NFV treatment of mice bearing tumor xenografts leads to improved oxygenation (10, 12). This is potentially clinically important because hypoxia is a factor associated with poor prognosis in many cancers, including HNSCC (13-15). Hypoxic cells require higher doses of radiation compared to oxic cells to achieve the same level of killing due to the requirement of oxygen to elicit maximal DNA damage through the oxidation of DNA and other target radicals (16). This leads us to one of our hypotheses that a major mechanism by which NFV improves the radiation response *in vivo* is by decreasing tumor hypoxia.

Determinants & Mechanisms of Nelfinavir Response

A phase I/II trial at Penn has been conducted in which NFV was combined with cisplatin-based (as with this protocol) chemotherapy and radiation for stage IIIA/B non-small cell lung cancer (17). The phase I trial showed that NFV given at a dose of 1250 mg (which was found to be the MTD) orally twice a day was well tolerated by these patients treated with chemoradiation. There were no dose limiting toxicities on this 16 patient trial, and no patients required dose attenuation of chemotherapy or nelfinavir. This trial did not test the idea than NFV can modulate tumor hypoxia or include hypoxia imaging. There are several methods that are available to measure hypoxia in human tumors including Eppendorf needle electrode and 2-nitroimidazole binding (18). 2-nitroimidazole drugs are reduced and form adducts with protein thiols in hypoxic cells (19).

1-H-1-(3-[18F] fluoro-2-hydroxypropyl)-2-nitroimidazole also known as

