8.3 Nelfinavir Reporting

Notifying the Penn IRB

The Penn IRB requires Principal Investigators to submit IRB required reports within 10 working days from the time the investigator becomes aware of the event. The event must meet the following requirements:

Report events in correlation to Nelfinavir if the event is grade 3 or higher, unexpected and the event is possibly, probably or definitely related to Nelfinavir.

Report events in correlation to study procedures if the event is grade 3 or higher, unexpected and the event is possibly, probably or definitely related to a study procedure.

If the event involved a death and indicates that participants or others are at risk of increased harm, investigators should report within 3 days.

All other events will be reported at the time of Continuing Review.

Notifying the Cancer Center DSMC (Cancer Research Studies Only)

AEs will be graded according to Common Terminology Criteria for Adverse Events (CTCAE) version 5.0 for reporting to the DSMC:

Report events in correlation to Nelfinavir within 10 working days of knowledge for all grade 3 or higher events regardless of attribution or expectedness.

Report events in correlation to study procedures within 10 working days of knowledge of all grade 3 or higher events regardless of attribution or expectedness.

If the event involved an unexpected death and indicates that participant or others are at risk of increased harm, investigators should report within 2 working days.

All other deaths within 30 days of knowledge. Deaths of subjects greater than 90 days from the last study treatment/intervention are not reportable unless a longer time frame is specified in the protocol.

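### Sections 7.1.1, 8.3 and 9.3 disagree on whether grade 3 or higher hematologic events are captured; if 7.1.1 is followed, added marrow toxicity would not be systematically assessed

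*Combined protocol and SAP*

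**What the plan says.** Three sections of the combined protocol and SAP bear on this.

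- **Section 7.1.1** says "Hematologic toxicities are expected and will not be followed as part of this trial" and leaves their management to the treating medical oncologist. It also gives a background figure: "Grade III hematologic toxicity occurs in approximately 50% of patients receiving combined chemoradiotherapy alone for head and neck cancer".
- **Section 8.3**, on reporting to the DSMC, says: "Report events in correlation to Nelfinavir within 10 working days of knowledge for all grade 3 or higher events regardless of attribution or expectedness". It has no hematologic exemption. The IRB rule in the same section is narrower and applies only if "the event is grade 3 or higher, unexpected and the event is possibly, probably or definitely related to Nelfinavir"; other events wait for Continuing Review.
- **Section 9.3** has laboratory results entered on a flow sheet and the CRF, and a toxicity form kept for each subject and evaluated up to the first standard follow-up visit after radiation. It too has no hematologic exemption.

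Section 6.7 provides for complete blood counts in all subjects, with timing left to the treating physicians. Section 7 contains no toxicity analysis and no safety boundary.

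**The concern.** The reason Section 7.1.1 gives for not following hematologic events is that they are expected. Section 8.3 says that expectedness does not matter for DSMC reporting. A coordinator with a grade 3 neutropenia in hand can find support for recording and reporting it, and equally for doing neither.

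The trial adds nelfinavir to a treatment that already causes severe hematologic toxicity in about half of patients. Against such a background a single case is unremarkable, and only a count across patients could show that the rate has risen. If 7.1.1 governs, nobody makes that count, and neither the DSMC nor the final report would have a systematic picture.

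There may also be an efficacy consequence. Under 7.1.1 the response to hematologic toxicity is a reduction in chemotherapy, so an uncounted excess could also mean less chemotherapy delivered. That would complicate the comparison of locoregional control with a historical rate.

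**Working it through.** The plan gives no toxicity calculation, so there is no figure to reproduce. The check has two parts.

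**1. The rules side by side, for a grade 3 or higher hematologic event**

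| Question | 7.1.1 | 8.3 (DSMC) | 9.3 |
|---|---|---|---|
| Is it captured? | Not followed in the trial | Reported | Laboratory result on CRF; toxicity form for each subject |
| Does expectedness matter? | Yes, it is the stated reason | No | Not mentioned |
| Does attribution matter? | Not mentioned | No, though the rule opens by referring to events connected with nelfinavir | The investigator verifies it |
| Hematologic exemption? | Yes | No | No |

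Only 7.1.1 exempts these events, and no text says which section prevails.

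**2. What full capture could show**

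Inputs:
- n = 28 (Study Summary; Section 7).
- Background rate p0 = 0.50, approximate (Section 7.1.1).
- One-sided 5% level. This is an assumption: the documents set no level for toxicity, and it is borrowed from the primary efficacy test in Section 7.
- Every patient has counts drawn often enough for an event to be found. This is also an assumption, since Section 6.7 leaves timing to discretion.

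Expected number of patients with an event at the background rate: 28 × 0.50 = 14.

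Exact (Clopper-Pearson) 95% interval for 14/28: the lower limit is the 0.025 quantile of Beta(14, 15) = 0.306 and the upper limit is the 0.975 quantile of Beta(15, 14) = 0.694, that is 31% to 69%.

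Upper-tail probability: P(X ≥ r) = Σ from k = r to 28 of C(28, k) p^k (1 − p)^(28 − k).

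At p = 0.50:
- P(X ≥ 18) = 0.092
- P(X ≥ 19) = 0.044

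The smallest count that meets the assumed 5% level is therefore 19 of 28. The chance of reaching it is:

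| True rate | P(X ≥ 19) |
|---|---|
| 60% | 26% |
| 65% | 46% |
| 70% | 68% |
| 75% | 86% |
| 80% | 96% |

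Sensitivity to the background rate: at 40% the threshold becomes 16 and power for a rise to 60% is about 70%; at 60% the threshold becomes 22 and power for a rise to 80% is 68%. Power for a 20-point rise is thus close to 70% across this range.

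**The case against.** The strongest reply is that this is a wording inconsistency and does not show that toxicity would go unseen. A reader might infer that the trial could not detect added marrow toxicity at all. The documents do not support that. If staff follow 8.3, grade 3 or higher events reach the DSMC; if they follow 9.3, laboratory results are on the CRF. The loss of information is conditional on 7.1.1 prevailing.

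Three further inferences also fail, and the reply is right about each.

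- *The HIV experience is the reason for not following these events.* In 7.1.1 the absence of hematologic toxicity in HIV patients and the 50% figure together explain why chemotherapy is the treatment to be reduced. The reason given for not following the events is only that they are expected.
- *There is no experience of nelfinavir with chemoradiation.* Section 1.1 describes a lung cancer trial of nelfinavir with cisplatin-based chemoradiation: "There were no dose limiting toxicities on this 16 patient trial, and no patients required dose attenuation of chemotherapy or nelfinavir". That is reassuring, but it is small and in another disease. The documents nowhere state that the combination is untested in head and neck cancer, and Sections 1.1 and 3.2 indicate that 15 subjects of this trial have already been imaged with the earlier tracer.
- *The two rules are flatly incompatible.* The 8.3 rule opens by referring to events connected with nelfinavir, which could be read as leaving out cytopenias put down to cisplatin. But the same sentence disregards attribution, so the phrase makes the scope unclear without supplying an exemption. The narrower IRB rule does not limit the DSMC rule; it shows that an expectedness limit was written where one was intended.

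The reply also fairly notes that 28 patients without a control arm give limited sensitivity, that Section 6.3 allows three-weekly cisplatin, weekly cisplatin or cetuximab while the 50% is not broken down by regimen, and that safety is not a listed objective. These points argue against a formal test. They do not argue against recording the events.

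**Conclusion.** The conflict is real and should be resolved. Section 7.1.1 states a rule that 8.3 and 9.3 contradict, and if it is followed, added marrow toxicity will not be systematically assessed.

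What is at stake is moderate. With full capture, a rise from 50% to 75% would probably be seen (86% power), a rise to 70% is less sure (68%), and a rise to 60% would probably be missed (26%). These figures rest on the assumed one-sided 5% level, the approximate 50% background and adequate blood-count frequency. The protocol also words the 50% as Grade III and does not say whether grade IV is included, so its match to a grade 3 or higher count is uncertain. For these reasons the tabulation should be descriptive, with the threshold of 19 as a guide to interpretation and not as a stopping or decision rule.

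**What to change.** Reconcile Sections 7.1.1, 8.3 and 9.3 on data capture:

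1. In 7.1.1, remove the statement that hematologic toxicities are not followed. Say instead that grade 3 or higher events found on routinely drawn counts are recorded on the existing toxicity form.
2. In Section 7, add a descriptive table giving the number and proportion of patients with such an event, an exact 95% confidence interval, and the approximate 50% beside it. State how many patients had counts drawn and how often, so that the proportion can be read in context.
3. In 8.3, state whether these events go to the DSMC within 10 working days or as periodic summaries, and what the reference to events connected with nelfinavir covers. At the quoted background the 10-day route means reports on about 14 of 28 patients, which is a practical argument for summaries.

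The cost is an amendment to the wording and a little more data entry, including retrieval from existing records if subjects already treated are to be tabulated. No new blood tests are called for, and no dose or management rule changes.

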7.1.2 Non-hematologic toxicities

Modifications in dose, frequency, and regimen of chemotherapy will be made for non-hematologic toxicity (such as hearing loss or rise in creatinine to $> 1.5 \times$ normal value). Nelfinavir will be held if during treatment, grade 4 mucositis, dysphagia, or odynophagia develops.

Regardless of cause, nelfinavir must be immediately held if during treatment, Grade \geq III hepatic function impairment develops as characterized by:

- Total bilirubin $> 3 \times$ ULN (upper limit of normal of local lab; corresponds to approx 2.7 mg/dl or 45.9 micromol/l) OR
- AST/ALT $> 5 \times$ ULN

AST, ALT, and total bilirubin must be verified no later than one week after the first assessment, and weekly thereafter until resolution to grade \leq I.

Dose administration must be held until recovery to grade \leq I for all three hepatic parameters, at which time dosing of nelfinavir can resume.

7.2 Correlative Laboratory Studies-Molecular Markers

All patients will have research blood samples drawn for biomarker analysis (prior to NFV therapy and again after lead-in).

8 Safety and Adverse Events

8.1 FMISO IND Investigator Reporting

Notifying the Radiology IND Support Office:

The Principal Investigator or designee will seek information from the subject in reference to any adverse events specific to imaging procedures or injection of the Investigational Agent that may have occurred, by specific questioning and, as appropriate, by examination.

Only events surrounding PET/CT study procedures and the Investigational Radiopharmaceutical Agent outlined in this protocol apply for reporting for the IND. Any treatment related events outlined in this protocol or otherwise will not

be collected or reported as part the imaging protocol and should be processed per the protocol and institutional policies.

It is the responsibility of the Principal Investigator to determine the grade, attribution and expectedness of the event.

Once an event surrounding study procedures and/or the Investigational Agent has been identified the PI should be contacted immediately to complete the AE & SAE Case Report Form.

- For the events in correlation to the Investigation Agent the event should be recorded on the AE & SAE Case Report Form if:
 - Record all events regardless grade, attribution or expectedness if the event occurred within 24 hours after the injection of FMISO.
- For the events in correlation to study procedures, the event should be recorded on the AE & SAE Case Report Form if:
 - Record all events regardless grade, attribution or expectedness.

A copy of the completed AE & SAE Case Report Form should be sent to the Radiology IND Support Office within 24 hours of knowledge for review by the IND Authorized Sponsor Representative.

The completed AE & SAE Case Report Form should be placed in the subject's chart and a copy placed in the Regulatory Binder (this is recommended for the preparation of the FDA IND Annual Report and IRB Continuing Review).

The clinical course of each event should be followed until resolution, stabilization, or until it has been determined that the investigational agent or study procedure is not the cause of the event.

Significant new information on ongoing adverse events should be provided promptly to the Radiology IND Support Office.

Notifying the Penn IRB

The Penn IRB requires Principal Investigators to submit IRB required reports within 10 working days from the time the investigator becomes aware of the event. The event must meet the following requirements:

- Report events in correlation to the Investigational Agent if:
 - The event occurred within 24 hours after the injection of FMISO.

- The event is grade 3 or higher, unexpected and the event is possibly, probably or definitely related to the Investigational Agent.

➤ Report events in correlation to study procedures if:

- The event is grade 3 or higher, unexpected and the event is possibly, probably or definitely related to a study procedure.

If the event involved a death and indicates that participants or others are at risk of increased harm, investigators should report within 3 days.

Follow instructions for report completion on the IRB website.

All other events will be reported at the time of Continuing Review.

Copies of each report and documentation of IRB notification and receipt will be sent to the Radiology IND Support Office and kept in the Clinical Investigator's study file.

Notifying the Cancer Center DSMC (Cancer Research Studies Only)

AEs will be graded according to Common Terminology Criteria for Adverse Events (CTCAE) version 5.0 for reporting to the DSMC:

➤ Report events in correlation to the Investigational Agent within 10 working days of knowledge if:

- The event occurred within 24 hours after the injection of FMISO.
- All grade 3 or higher events regardless of attribution or expectedness.

➤ Report events in correlation to study procedures within 10 working days of knowledge if:

- All grade 3 or higher events regardless of attribution or expectedness.

If the event involved an unexpected death and indicates that participant or others are at risk of increased harm, investigators should report within 2 working days.

All other deaths within 30 days of knowledge. Deaths of subjects greater than 90 days from the last study treatment/intervention are not reportable unless a longer time frame is specified in the protocol.

Follow instructions for report completion on the Cancer Center website.

Copies of each report and documentation of Cancer Center DSMC notification and receipt will be sent to the Radiology IND Support Office and kept in the Clinical Investigator's study file.

Sponsor Reporting

Notifying the FDA

The study sponsor is required to report certain study events in an expedited fashion to the FDA. These written notifications of adverse events are referred to as IND Safety Reports. The following describes the safety reporting requirements by timeline for reporting and associated type of event:

Events in correlation to the Investigational Agent:

Report within 7 calendar days

- The event occurred within 24 hours after the injection of FMISO.
- Associated with the use of the study drug.
- Unexpected.
- Fatal or life-threatening.

Report within 15 calendar days

- The event occurred within 24 hours after the injection of FMISO.
- Associated with the use of the study drug.
- Unexpected.
- Serious, but not fatal or life-threatening.

-OR-

- A previous adverse event that was not initially deemed reportable but is later found to fit the criteria for reporting (reporting within 15 calendar days from when event was deemed reportable).

Any finding from tests in laboratory animals that:

- Suggest a significant risk for human subjects including reports of mutagenicity, teratogenicity, or carcinogenicity.

Notifying Participating Investigators

It is the responsibility of the study sponsor to notify all participating investigators, in a written IND safety report, of any adverse event associated with the use of the drug that is both serious and unexpected, as well as any finding from tests in laboratory animals that suggest a significant risk for human subjects. Additionally, sponsors are also required to identify in IND safety reports all previous reports concerning similar adverse events and to analyze the significance of the current event in light of the previous reports.

Additional Sponsor Reporting Requirements

Sponsors are also required to identify in IND safety reports all previous reports concerning similar adverse events and to analyze the significance of the current event in light of the previous reports.

Other IRB Reportable Events:

- Any adverse event that would cause the sponsor to modify the investigators brochure, protocol or informed consent form, or would prompt other action by the IRB to assure protection of human subjects.
- Information that indicates a change to the risks or potential benefits of the research, in terms of severity or frequency, for example:
 - An interim analysis indicates that participants have a lower rate of response to treatment than initially expected.
 - Safety monitoring indicates that a particular side effect is more severe, or more frequent than initially expected.
 - A paper is published from another study that shows that an arm of your research study is of no therapeutic value.
- Change in FDA safety labeling or withdrawal from marketing of a drug, device, or biologic used in a research protocol.
- A breach of confidentiality.
- Change to the protocol taken without prior IRB review to eliminate apparent immediate hazard to a research participant.
- Incarceration of a participant when the research was not previously approved under Subpart C and the investigator believes it is in the best interest of the subject to remain on the study.
- Complaint of a participant when the complaint indicates unexpected risks or the complaint cannot be resolved by the research team.
- Protocol violation (meaning an accidental or unintentional deviation from the IRB approved protocol) that in the opinion of the investigator placed one or more participants at increased risk, or affects the rights or welfare of subjects.
- **Exceptions:** A study exception is a one time, intentional action or process that departs from the IRB and CTSRMC approved study protocol, intended for one occurrence. If the action disrupts the study progress, such that the study design or outcome (endpoints) may be compromised, or the action compromises the safety and welfare of study subjects, advance documented IRB and DSMC approval is required. For this in-house study with a sponsor monitor, approval will be obtained from the study sponsor (IND Support Office) prior to submitting the exception request to the IRB and DSMC.
- **Deviations:** A study design deviation is a one time, unintentional action or process that departs from the IRB and CTSRMC approved study protocol,

involving one incident and identified retrospectively, after the event occurred. If the impact on the protocol disrupts the study design, may affect the outcome (endpoints) or compromises the safety and welfare of the subjects, the deviation will be reported to the DSMC and IND Support Office within 5 business days and the IRB within 10 business days.

8.2 $^{18}\text{F-FMISO}$ and FDG PET/CT

Pregnancy Clause

The effects of $^{18}\text{F-FMISO}$ on unborn children, children who are breast-feeding and the health of the mother are unknown. For this reason, subjects who are pregnant must inform the investigator(s) and understand that she will not be included in the study. Women of childbearing age will have a pregnancy test before making a decision about participating in the study. The cost of the exam is part of regular cancer care and may be done even they do not join the study.

IV Contrast Risks & Procedures Clause

There is a risk that multiple needle-sticks will be necessary in order to ensure proper placement of the Intravenous line. There is a small risk of infection at the site the catheter is placed or there may be a small amount of pain or bruising associated with the placement of the Intravenous catheter.

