4.6 Off-Study Criteria

- Extraordinary Medical Circumstances. If at any time the constraints of this protocol are detrimental to the subject's health, the subject will be removed from protocol therapy. In this event, the reasons for withdrawal will be documented.
- Subject's refusal to continue treatment. In this event, the reasons for withdrawal will be documented.
- Any patient who experiences any Grade III or higher toxicity related to ¹⁸F-FMISO and not related to the underlying disease.
- Patients will be considered "off-study" at the completion of study procedures. This will occur at the completion of 3 month follow up PET/CT.
- Patients may be taken off study at any time at the discretion of the Principal Investigator
- Every effort will be made to follow subjects off study for toxicity and survival.

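### Section 8.1 applies its 24-hour limit even to FMISO events judged related, so late serious unexpected events fall outside agent-event recording and expedited FDA reporting

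*Combined protocol and SAP*

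**What the plan says.** Section 8.1 (FMISO IND Investigator Reporting) separates events tied to the imaging agent from events tied to study procedures. For agent events the instruction for the AE & SAE form is "Record all events regardless grade, attribution or expectedness if the event occurred within 24 hours after the injection of FMISO". That form goes to the Radiology IND Support Office within 24 hours of knowledge.

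The expedited rules for agent events repeat the limit. "The event occurred within 24 hours after the injection of FMISO" stands in the IRB list, the DSMC list, and both FDA lists (7 and 15 calendar days). In the FDA lists the next condition is "Associated with the use of the study drug", followed by unexpectedness and then by severity: fatal or life-threatening for 7 days, otherwise serious for 15 days.

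Two rules have no time limit:

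- Under Notifying Participating Investigators, also in 8.1, the sponsor must issue a written IND safety report on "any adverse event associated with the use of the drug that is both serious and unexpected".
- Section 4.6 lists among its off-study criteria "Any patient who experiences any Grade III or higher toxicity related to" FMISO rather than to the underlying disease.

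For the IRB there is a non-expedited route: "All other events will be reported at the time of Continuing Review".

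**The concern.** A time window is a sensible filter when events are collected whatever their cause, because it stands in for attribution. Once an event has been judged related, the window has no such job left. It then only excludes related events that occur late.

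Two things are at stake. First, one section gives the sponsor two different triggers for an IND safety report on the same event, depending on the recipient. Second, FMISO is given repeatedly. Section 6.5 schedules one injection before any therapy and another after 7-14 days of nelfinavir alone, and the Introduction gives six patients a further baseline injection. A delayed related reaction to one injection is relevant to the next, and the FMISO form need not hold it. The protocol itself treats hypersensitivity as a possibility: 4.2.18 excludes patients with a history of allergy to metronidazole because of its structural similarity to FMISO.

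**Working it through.** The plan gives no figure to reproduce here. The check sets the rules side by side and adds two small pieces of arithmetic.

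**Are the conditions joint?** Yes. The IRB rule introduces its list as requirements that the event must meet. In the FDA 15-day list the one alternative is set off by an explicit OR, so the other items are cumulative. Read as alternatives, unexpectedness alone would trigger an FDA report, which cannot be meant.

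**Test case.** Take a serious, non-fatal, grade 3, unexpected, FMISO-associated event 30 hours after injection.

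| Rule | Time limit | Other conditions | Triggered at 30 h? |
|---|---|---|---|
| 8.1 form, agent events | 24 h | none | No |
| 8.1 IRB, 10 working days, agent events | 24 h | grade 3 or above, unexpected, at least possibly related | No; goes to continuing review |
| 8.1 DSMC, 10 working days, agent events | 24 h | grade 3 or above, any cause | No |
| 8.1 FDA, 15 days | 24 h | associated, unexpected, serious | No |
| 8.1 notice to participating investigators | none | associated, unexpected, serious | Yes |
| 4.6 off-study criterion | none | related, Grade III or above | Yes |

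A fatal event at 30 hours fails the FDA 7-day list in the same way.

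**What the limit does in the FDA lists.** Write A for associated, U for unexpected, S for serious and W for within 24 hours. The FDA 15-day line requires A, U, S and W. The investigator line requires A, U and S. The difference is exactly the set A, U, S and not W: late, associated, serious, unexpected events. Section 8.1 calls the FDA notifications IND Safety Reports and uses the same term for the notice to investigators, so one kind of report has two triggers.

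**Does the late-fit item help?** The 15-day list also covers an event not thought reportable at first that later proves to fit the criteria. Those criteria include the 24 hours, so an event at 30 hours still does not fit.

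**Section 4.6.** Its rule and the reporting window can both be followed, so there is no literal contradiction. The tension is that 4.6 acts on related toxicity at any time, while the FMISO form need not record that toxicity after 24 hours.

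**Time to the next injection.** The first scan precedes all therapy and the later one follows 7-14 days of nelfinavir, so the interval is at least 7 × 24 = 168 h to 14 × 24 = 336 h. The window covers 24/168 = 14.3% to 24/336 = 7.1% of it, leaving 6 to 13 days outside. These are shares of calendar time, not of risk. For the six test-retest patients the interval between the two baseline injections is not stated.

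**Radioactive decay.** With a half-life of about 110 minutes (5.8.1), 24 × 60/110 = 13.1 half-lives pass in 24 hours, leaving about 0.01% of the activity. That could motivate a short window, but the protocol does not give this reason, and it does not bear on an event already judged related.

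**The case against.** The strongest reply is that late events have other routes, and this is largely true:

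- 8.1 sends remaining events to the IRB at continuing review.
- 8.1 sets separate timelines for deaths, with a 90-day limit at the DSMC.
- 8.1 records study-procedure events on the same form with no window.
- 8.1 lists other IRB-reportable events without a window.
- 8.3 sends grade 3 or higher events to the DSMC under the nelfinavir heading, whatever their attribution.
- 9.3 keeps toxicity forms, with attribution verified, to the first follow-up visit after radiation.

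A reader might therefore infer too much if they concluded that late FMISO events are recorded nowhere, or are hidden. The documents do not support that.

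What these routes do not do is close the specific gap. Continuing review is not expedited. The nelfinavir rule has no clear place for a reaction after the first scan, which precedes nelfinavir. Nothing in 9.3 sends toxicity forms to the FMISO IND office. A late reaction classed as a procedure event would reach the form, but the FDA lists are written for agent events. The general commitment in section 11 to FDA regulations does not alter the explicit lists that staff would follow.

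Three other strong readings also fail:

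- That 4.6 is contradicted. It is itself a patient-level safeguard without a time limit, and the relation is one of tension.
- That every trial patient is affected. Section 3.3 says the initial 15 subjects were imaged with EF5, and 3.1 lets the investigator excuse a patient from PET.
- That most of the risk lies outside the window. That would need a roughly constant hazard over 7-14 days, which nothing in the documents supports. The injected mass is at most 15 µg.

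**Conclusion.** The point holds as an inconsistency in the safety-reporting text. In 8.1 the 24-hour limit governs recording of FMISO-agent events and expedited IRB, DSMC and FDA reporting, even for events judged related. In the FDA lists it removes late, associated, serious, unexpected events, which conflicts with the unlimited investigator-notification duty in the same section and is in tension with 4.6. No other route restores agent-event recording or expedited FDA reporting.

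Its practical size cannot be computed. It concerns only subjects imaged with FMISO: if the 28 planned subjects include the 15 imaged with EF5, that is at most 28 − 15 = 13, but section 7 can also be read as 28 counted from the amendment. The number of late related reactions is not given and may be small. The primary endpoint and its analysis are unaffected.

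The conclusion assumes that the listed conditions are cumulative, as the layout of the lists indicates.

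**What to change.** State in 8.1 that the 24-hour window applies only to events captured whatever their cause, and remove it for events judged at least possibly related to FMISO:

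- **Form:** all events within 24 hours, plus related events at any time.
- **IRB:** delete the window, since the list already requires relatedness.
- **DSMC:** keep the window for grade 3 or higher events of any cause, and add related grade 3 or higher events at any time.
- **FDA 7-day and 15-day lists:** delete the window, since both already require association with the drug.

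The FDA lists would then match the investigator-notification paragraph, and the form would hold the information on which 4.6 depends. No dose, procedure or off-study rule needs to change.

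The cost is an amendment to the wording of 8.1, agreed with the IND office, and probably a few more forms. If the sponsor does intend the window to cover related events, 8.1 should say so, give the reason, and reconcile it with the investigator-notification paragraph and 4.6.
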